5.3.2 Eliciting Adverse Event Information

A consistent methodology of non-directive questioning should be adopted for eliciting adverse event information at all patient evaluation timepoints. Examples of non-directive questions include the following:

"How have you felt since your last clinic visit?"

"Have you had any new or changed health problems since you were last here?"

5.3.3 Assessment of Severity of Adverse Events

The adverse event severity grading scale indicated in [Table 4](#) will be used for assessing adverse event severity. Laboratory values determined as an adverse event should be graded as per [Appendix 6](#), which is based on the NCI CTCAE (v5.0).

Table 4 Adverse Event Severity Grading Scale

Severity	Description
Mild	Discomfort noticed, but no disruption of normal daily activity
Moderate	Discomfort sufficient to reduce or affect normal daily activity
Severe	Incapacitating with inability to work or to perform normal daily activity

Note: Regardless of severity, some events may also meet seriousness criteria.

Refer to definition of a serious adverse event (see Section [5.2.2](#)).

5.3.4 Assessment of Causality of Adverse Events

Investigators should use their knowledge of the patient, the circumstances surrounding the event, and an evaluation of any potential alternative causes to determine whether an adverse event is considered to be related to the study drug, indicating "yes" or "no" accordingly. The following guidance should be taken into consideration (see also [Table 5](#)):

- Temporal relationship of event onset to the initiation of study drug
- Course of the event, with special consideration of the effects of dose reduction, discontinuation of study drug, or reintroduction of study drug (as applicable)
- Known association of the event with the study drug or with similar treatments
- Known association of the event with the disease under study
- Presence of risk factors in the patient or use of concomitant medications known to increase the occurrence of the event
- Presence of non-treatment-related factors that are known to be associated with the occurrence of the event

Table 5 Causal Attribution Guidance

Is the adverse event suspected to be caused by the study drug on the basis of facts, evidence, science-based rationales, and clinical judgment?	
YES	There is a plausible temporal relationship between the onset of the adverse event and administration of the study drug, and the adverse event cannot be readily explained by the patient's clinical state, intercurrent illness, or concomitant therapies; and/or the adverse event follows a known pattern of response to the study drug; and/or the adverse event abates or resolves upon discontinuation of the study drug or dose reduction and, if applicable, reappears upon re-challenge.
NO	An adverse event will be considered related, unless it fulfills the criteria specified below. Evidence exists that the adverse event has an etiology other than the study drug (e.g., preexisting medical condition, underlying disease, intercurrent illness, or concomitant medication); and/or the adverse event has no plausible temporal relationship to administration of the study drug (e.g., cancer diagnosed 2 days after first dose of study drug).

5.3.5 Procedures for Recording Adverse Events

Investigators should use correct medical terminology/concepts when recording adverse events on the Adverse Event eCRF. Avoid colloquialisms and abbreviations.

Only one adverse event term should be recorded in the event field on the Adverse Event eCRF.

5.3.5.1 Injection Reactions

Adverse events that occur during or within 24 hours after study drug administration should be captured as individual signs and symptoms on the Adverse Event eCRF rather than an overall diagnosis (e.g., record dyspnea and hypotension as separate events rather than a diagnosis of IT bolus-related reaction or anaphylactic reaction).

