5.1.1 Known Risks Associated with Lumbar Puncture

Post-lumbar puncture syndrome, spinal hematoma, and meningitis (see Sections [5.1.1.1](#) through [5.1.1.3](#)) are potential risks associated with lumbar puncture.

In the completed Phase I/IIa study, the most commonly reported adverse events across all treatment groups (RO7234292, n=34; placebo, n=12) were procedural pain (54% of patients) and post-lumbar puncture syndrome (37% of patients).

In the recently completed Phase II OLE study BN40697, potential LP procedure-associated selected AEs were reported with similar incidence across the cohorts despite the difference in dosing frequency (16 patients [69.6%] in the Q4W cohort and 17 patients [73.9%] in the Q8W cohort). Overall, the most frequently reported event was procedural pain (41.3%). In the ongoing Phase III study BN40423, patients enrolled under Protocol Versions 1–3 (receiving Q4W blinded treatment) were discontinued following discontinuation of the Q4W dosing. These patients' treatment assignments are now unblinded and hereby referred to as original design cohort (ODC). In the ODC, potential LP procedure associated selected AEs were reported with similar incidence across the three cohorts (17 patients [47.2%] in the placebo cohort, 14 patients [40%] in the Q4W cohorts, and 17 patients [47.2%] in the Q8W cohort). Overall, the events reported with highest incidence were procedural pain and post-LP syndrome (14% each).

As of 7 August 2020, in the ongoing Study BN40955, potential LP procedure associated selected AEs were reported in 30 patients [22.9%] in the Q8W cohort and 11 patients [15.1%] in the Q16W cohort. Overall the most frequently reported event was procedural pain (9.2% in the Q8W cohort and 4.1% in the Q16W cohort).

Many of the complications associated with lumbar puncture can be avoided by the mandatory use of a 24G atraumatic needle with a stylet, adherence to procedural

guidelines (see lumbar puncture manual and instructional video), and careful assessment of the patient, including neurologic examination with fundoscopy both prior to and post-lumbar puncture procedure. Lumbar puncture should be avoided when a contraindication is present.

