5.1.1.1 Post-Lumbar Puncture Syndrome

RO7234292 is delivered directly to the CNS by IT lumbar puncture injection. Post-lumbar puncture syndrome (e.g., headaches, nausea, vomiting, infection, hemorrhage, nerve irritation pain) can occur with IT administration. Experience to date with post-lumbar puncture syndrome, as reported in the completed Phase I/IIa study, includes headache, which occurred after 10% of procedures and was transient and mild in the vast majority of patients.

In the recently completed Phase II OLE Study BN40697, post-LP syndrome events (such as post-LP syndrome, headache, migraine, nausea, vomiting or procedural headache) occurring within 5 days of LP were reported in 9 patients (39.1%) in the Q4W cohort and 13 patients (56.5%) in the Q8W cohort.

In Study BN40423 ODC, post-LP syndrome events (post-LP syndrome, headache, migraine, nausea, vomiting or procedural headache) occurring within 5 days of LP were

reported in 14 patients (38.9%) in the placebo cohort, 8 patients (22.9%) in the Q4W cohort and 14 patients (38.9%) in the Q8W cohort.

As 7 August 2020, in the ongoing Study BN40955, post-LP syndrome events (such as post-LP syndrome, headache, migraine, nausea, vomiting or procedural headache) occurring within 5 days of LP were reported in 7 patients (5.3%) in the Q8W cohort and 2 patients (2.7%) in the Q16W cohort.

The majority of these events were mild or moderate and non-serious. No events led to treatment interruption or discontinuation.

Patients should walk post-lumbar procedure (see Section 4.3.2.1). However, if a patient develops a headache after the lumbar puncture with characteristic features, which makes walking intolerable, the patient should be encouraged to first sit down and if the headache persists then *the patient should* lie in a comfortable position, which is most likely in the supine position owing to the postural nature of the symptoms. Supportive treatment may include rehydration, consumption of caffeinated drinks, simple analgesics, opioids, and antiemetics. If these conservative measures fail, more specific measures may be indicated.

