5.1.2.2 Elevations in CSF WBCs and Protein

The CSF WBC elevations were also observed in the chronic non-human primate study with slight increases over time. Increases were mild, and there was no apparent dose dependency.

CSF protein and WBC increases have been observed in the RO7234292 program.

In Study BN40697, one patient was diagnosed with chemical meningitis (SUSAR case) in the Q4W cohort. As of 4 October 2020, in the ongoing Study BN40955, one patient experienced aseptic meningitis (clinically not infectious) and one patient experienced arachnoiditis, in the Q8W cohort.

For details on CSF proteins and WBC laboratory values and non-serious AEs of CSF WBC and protein increases, please refer to the RO7234292 Investigator's Brochure.

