5.3.5.2 Diagnosis versus Signs and Symptoms

For adverse events other than injection reactions (see Section 5.3.5.1), a diagnosis (if known) should be recorded on the Adverse Event eCRF rather than individual signs and symptoms (e.g., record only liver failure or hepatitis rather than jaundice, asterixis, and elevated transaminases). However, if a constellation of signs and/or symptoms cannot be medically characterized as a single diagnosis or syndrome at the time of reporting, each individual event should be recorded on the Adverse Event eCRF. If a diagnosis is subsequently established, all previously reported adverse events based on signs and symptoms should be nullified and replaced by one adverse event report based on the single diagnosis, with a starting date that corresponds to the starting date of the first symptom of the eventual diagnosis.

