6.7 SAFETY ANALYSES

The safety population (see Section [6.1](#)) will be the primary population for all analyses of safety data. Incorrect treatment assignments (patients who received a treatment different than their planned randomized treatment) will be summarized and the impact on the safety assessment will be discussed.

For all safety analyses, patients enrolled prior to implementation of the Version 4 of the protocol will be summarized separately.

All verbatim adverse event terms will be mapped to MedDRA thesaurus terms. The adverse event severity grading scale indicated in [Table 4](#) will be used for assessing adverse event severity. Laboratory values determined as an adverse event should be graded as per [Appendix 6](#), which is based on the NCI CTCAE (v5.0).

All safety data, including adverse events, laboratory tests, CSSR-S, MoCA, ECG, and vital signs will be reported in individual listings and summarized by treatment for each assessment time using descriptive statistics. For continuous variables, both the original value as well as the change from baseline will be reported.

The incidence of adverse events will be summarized on the basis of body systems and dictionary preferred terms. The incidence of adverse events by severity and relationship to study drug or study procedure and incidence of marked abnormal laboratory test results will be provided.

The iDMC will review safety data throughout the study. Analyses required for the iDMC data review will be performed as described in the iDMC Charter.

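### Section 5.3.5.1 has adverse events within 24 hours of dosing entered as symptoms, so a specific diagnosis with onset in that window may be missing from the preferred-term tables

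*Protocol*

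**What the plan says.** Section 5.3.5.1 (Injection Reactions) states: "Adverse events that occur during or within 24 hours after study drug administration should be captured as individual signs and symptoms". Its example tells sites to "record dyspnea and hypotension as separate events rather than a diagnosis of IT bolus-related reaction or anaphylactic reaction". The sentence sets no condition on relatedness, specificity or seriousness. Its verb is *should*.

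Section 5.3.5.2 gives the opposite rule for everything else: "For adverse events other than injection reactions (see Section 5.3.5.1), a diagnosis (if known) should be recorded on the Adverse Event eCRF". The same section goes on: "If a diagnosis is subsequently established, all previously reported adverse events based on signs and symptoms should be nullified", with a single diagnosis entered in their place and dated from its first symptom.

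Section 5.3.5 allows one term per event field. Section 6.7 describes the tabulation: "The incidence of adverse events will be summarized on the basis of body systems and dictionary preferred terms".

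Section 4.5.5 and Appendix 1b keep lumbar punctures at the early termination visit and the Week 101 visit, with no drug given.

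**The concern.** The two recording rules do not meet cleanly. Section 5.3.5.1 defines its scope by time since injection, while Section 5.3.5.2 defines the exclusion by the label of injection reaction and points back to 5.3.5.1. A site that follows the words has no written route by which a specific diagnosis beginning inside the 24-hour window enters the database as that diagnosis, even once it is established.

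The diagnoses concerned include risks that the protocol itself names in Sections 5.1.1 and 5.1.2: post-lumbar-puncture syndrome, meningitis and arachnoiditis. If such an event is entered as headache, vomiting and pyrexia, a preferred-term table shows common symptoms that any punctured patient may report, and the diagnosis row is short by one.

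The trigger is administration of study drug, so it does not cover punctures done without dosing. The same complication then falls under different rules according to whether an injection was given.

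**Working it through.** No power, alpha or sample-size figure depends on this point. The check is mainly a comparison of text, with simple counts.

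**1. The rules side by side, read literally.**

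| Event | Section | Entry |
|---|---|---|
| Specific diagnosis, onset within 24 h of a dosing puncture | 5.3.5.1 | Component symptoms; no replacement rule stated |
| Same diagnosis, onset later | 5.3.5.2 | Diagnosis, replacing symptoms |
| Same diagnosis, onset within 24 h of a non-dosing puncture | 5.3.5.2 | Diagnosis, replacing symptoms |

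Anaphylactic reaction is the clearest case, because the example names it. For meningitis, arachnoiditis and post-lumbar-puncture syndrome, the outcome depends on reading the time window as the scope of the rule.

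**2. Whether another section rescues the diagnosis.** Section 5.4 requires a changed diagnosis to be reported, but only for serious events, events of special interest and pregnancies. Section 5.2.3 limits events of special interest to potential liver injury and suspected transmission of an infectious agent by the drug. Serious events go on the same Adverse Event eCRF (Section 5.4.2.2), to which 5.3.5.1 applies. Section 5.4 therefore does not change what 5.3.5.1 asks sites to enter.

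**3. Exposure to the rule by arm** (Section 3.1.1, Table 1, planned injections).
- Q8W: 2 + 11 = 13.
- Q16W: 2 + 5 active + 6 placebo = 13.
- Placebo: 2 + 11 = 13.

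Thirteen one-day windows over 100 weeks are 13/700 = 1.9% of follow-up. Complications of puncture can be expected to cluster near the puncture, so this calendar share is not the share of cases affected.

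**4. What the protocol's own counts show** (Sections 5.1.1 and 5.1.1.1, original design cohort).
- Denominators: 17/0.472 = 36 placebo, 14/0.40 = 35 Q4W, 17/0.472 = 36 Q8W, in total 107.
- Post-lumbar-puncture syndrome as a reported term: 14%, about 15/107.
- The grouped set of terms within 5 days of puncture was "reported in 14 patients (38.9%) in the placebo cohort, 8 patients (22.9%) in the Q4W cohort and 14 patients (38.9%) in the Q8W cohort": (14 + 8 + 14)/107 = 36/107 = 33.6%.

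The first count shows that this diagnosis is being entered. The second is a wider set of terms over a longer window, so the gap between the two does not measure the 24-hour rule.

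**5. How a loss would scale.** Let p be the true incidence of a diagnosis and f the share of affected patients whose diagnosis is split into symptoms because onset was within 24 hours. The tabulated incidence is p(1 − f). The documents do not give f. For an assumed p of 14%:

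| f | Tabulated |
|---|---|
| 0 | 14% |
| 0.25 | 10.5% |
| 0.5 | 7% |
| 0.75 | 3.5% |
| 1 | 0% |

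The whole range is open.

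**The case against.** The strongest reply is that the rule is narrower than its first sentence. It stands under the heading of injection reactions, says *should*, and takes acute reactions as its example. Section 5.3.5.2 excludes injection reactions, not all events within 24 hours. A meningitis confirmed days later can be brought into the window only by dating it from its first symptom, and that dating clause belongs to the replacement rule in 5.3.5.2. This reading is available, but the text does not compel it, and it does not help anaphylactic reaction.

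The reply continues that the diagnoses do appear: post-lumbar-puncture syndrome in this study, and meningitis and arachnoiditis elsewhere in the program. This stands against any claim that under-counting has been shown. It does not show that the rule is harmless, since the recorded cases may have begun later, or sites may have departed from the wording. In the latter case recording is inconsistent.

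No study drug has been given since 22 March 2021, so rewording alone changes little from now on. This also stands, and it moves the remedy to data already collected. Two further objections stand: grouped-term tables can be left to the SAP, and Section 6.7 plans no comparison of dosing with non-dosing periods, so the difference in recording harms no stated comparison.

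**Conclusion.** Section 5.3.5.1 is worded too broadly and needs to be reconciled with 5.3.5.2. Followed literally, the two sections can keep a specific diagnosis with onset in the 24-hour window out of the preferred-term tables, and they record the same complication differently after dosing and non-dosing punctures. The documents do not give the size of any loss. It depends on onset times and on how sites applied the rule.

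Three stronger readings are tempting and are not supported.

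- A reader might take 14% against 33.6% as the under-count. The two figures cover different events and different windows.
- A reader might project from the extension study BN40955, where "one patient experienced aseptic meningitis (clinically not infectious) and one patient experienced arachnoiditis, in the Q8W cohort", to a number of cases lost per arm. Those two cases were recorded as diagnoses, in another study, and any share with onset in 24 hours would be an assumption.
- A reader might infer that the active-versus-placebo contrast is pulled towards zero. With 13 planned injections in every arm, the schedule gives no difference between arms in exposure to the rule. If the same share f applied in both arms, the absolute difference would become (1 − f) times its true value and the ratio would not change. No document shows that f is above zero for a drug-caused diagnosis.

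**What to change.** Limit Section 5.3.5.1 to non-specific injection reactions for which no diagnosis is established. State that the replacement rule of 5.3.5.2 applies to any specific diagnosis, whatever its onset time, and after dosing and non-dosing punctures alike. This changes recording only and leaves clinical management untouched.

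Because dosing has stopped, apply the reconciled rule to the data in hand. Run a programmed query, blind to arm, that finds clusters of symptom entries starting within 24 hours of an injection and asks the site whether a diagnosis was established. Site staff remain blinded under Section 4.2, so they should give the answers. The sponsor is unblinded (Sections 3.1.2 and 4.2), so the definition of a cluster and the query text must be fixed without reference to treatment and applied to all arms.

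The cost is a few sentences of protocol wording, one query and some re-coding of existing entries. The main risk is selective re-coding, which the arm-blind query rule is there to prevent.

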5.3.5.2 Diagnosis versus Signs and Symptoms

For adverse events other than injection reactions (see Section 5.3.5.1), a diagnosis (if known) should be recorded on the Adverse Event eCRF rather than individual signs and symptoms (e.g., record only liver failure or hepatitis rather than jaundice, asterixis, and elevated transaminases). However, if a constellation of signs and/or symptoms cannot be medically characterized as a single diagnosis or syndrome at the time of reporting, each individual event should be recorded on the Adverse Event eCRF. If a diagnosis is subsequently established, all previously reported adverse events based on signs and symptoms should be nullified and replaced by one adverse event report based on the single diagnosis, with a starting date that corresponds to the starting date of the first symptom of the eventual diagnosis.

5.3.5.3 Adverse Events That Are Secondary to Other Events

In general, adverse events that are secondary to other events (e.g., cascade events or clinical sequelae) should be identified by their primary cause, with the exception of

severe or serious secondary events. A medically significant secondary adverse event that is separated in time from the initiating event should be recorded as an independent event on the Adverse Event eCRF. For example:

- If vomiting results in mild dehydration with no additional treatment in a healthy adult, only vomiting should be reported on the eCRF.
- If vomiting results in severe dehydration, both events should be reported separately on the eCRF.
- If a severe gastrointestinal hemorrhage leads to renal failure, both events should be reported separately on the eCRF.
- If dizziness leads to a fall and consequent fracture, all three events should be reported separately on the eCRF.
- If neutropenia is accompanied by an infection, both events should be reported separately on the eCRF.

All adverse events should be recorded separately on the Adverse Event eCRF if it is unclear as to whether the events are associated.

5.3.5.4 Persistent or Recurrent Adverse Events

A persistent adverse event is one that extends continuously, without resolution, between patient evaluation timepoints. Such events should only be recorded once on the Adverse Event eCRF. The initial severity (intensity or grade) of the event will be recorded at the time the event is first reported. If a persistent adverse event becomes more severe, the most extreme severity should also be recorded on the Adverse Event eCRF. If the event becomes serious, it should be reported to the Sponsor immediately (i.e., no more than 24 hours after learning that the event became serious; see Section 5.4.2 for reporting instructions). The Adverse Event eCRF should be updated by changing the event from "non-serious" to "serious," providing the date that the event became serious, and completing all data fields related to serious adverse events.

A recurrent adverse event is one that resolves between patient evaluation timepoints and subsequently recurs. Each recurrence of an adverse event should be recorded as a separate event on the Adverse Event eCRF.

5.3.5.5 Abnormal Laboratory Values

Not every laboratory abnormality qualifies as an adverse event. A laboratory test result must be reported as an adverse event if it meets any of the following criteria:

- Is accompanied by clinical symptoms
- Results in a change in study treatment (e.g., dosage modification, treatment interruption, or treatment discontinuation)
- Results in a medical intervention (e.g., potassium supplementation for hypokalemia) or a change in concomitant therapy
- Is clinically significant in the investigator's judgment

It is the investigator's responsibility to review all laboratory findings. Medical and scientific judgment should be exercised in deciding whether an isolated laboratory abnormality should be classified as an adverse event.

If a clinically significant laboratory abnormality is a sign of a disease or syndrome (e.g., ALP and bilirubin $5 \times$ ULN associated with cholestasis), only the diagnosis (i.e., cholestasis) should be recorded on the Adverse Event eCRF.

If a clinically significant laboratory abnormality is not a sign of a disease or syndrome, the abnormality itself should be recorded on the Adverse Event eCRF, along with a descriptor indicating whether the test result is above or below the normal range (e.g., "elevated potassium," as opposed to "abnormal potassium"). If the laboratory abnormality can be characterized by a precise clinical term per standard definitions, the clinical term should be recorded as the adverse event. For example, an elevated serum potassium level of 7.0 mEq/L should be recorded as "hyperkalemia."

Observations of the same clinically significant laboratory abnormality from visit to visit should only be recorded once on the Adverse Event eCRF (see Section [5.3.5.4](#) for details on recording persistent adverse events).

